5.7 Withdrawal of Subjects

Participants are systematically notified that they are free to withdraw from the study at any time. No special provisions for withdrawal are necessary. Participants are free to retain other usual amputation-related care without interruption. As this study examines the feasibility of a self-management intervention in the VA Amputation System of Care, it is highly unusual that a participant would be withdrawn from the research without consent. The study is interested in tracking withdraws and citing reasons for withdrawal. Investigator-initiated withdrawals will be evaluated and discussed by site PIs and the lead PI/SC and/or Co-PI. The PI/SC and/or site PI may also suspend enrollment of an individual participant if it is determined it was not in his/her best interest to continue, or it was not in the best interest of the intervention group (e.g. participant was consistently combative and argumentative in group). All reasons for investigator initiated withdrawals will be documented in the notes section of the eCRF.

7.0 Reporting

6.1 Adverse Events

Definitions

An **Adverse Event (AE)** is defined as any unfavorable and unintended diagnosis, sign (including an abnormal laboratory finding), symptom, or disease temporarily associated with the study intervention, which may or may not be related to the intervention. AEs include any new events not present during the pre-intervention period or events that were present during the pre-intervention period but have increased in severity.

Anticipated AEs are those that might reasonably be expected to occur in this population with significant medical comorbidity and can include, but are not necessarily limited to, re-hospitalization, revision amputation, conversion to higher-level amputation, contralateral limb amputation, pain, stroke, myocardial infarction, deep venous thrombosis, dialysis, superficial or deep infection, and death. Each site will maintain a log of all anticipated AEs, including those captured on eCRFs through medical record review.

An **unanticipated adverse event (UAE)** is an adverse event that is not expected to occur in this population with significant medical comorbidity.

Unanticipated problems (UAP), also the phrase “unanticipated problems involving risks to subjects or others”, in general, include any incident, experience, or outcome that meets all of the following:

1. Unexpected (in terms of nature, severity, or frequency) given (a) the research procedures that are described in the protocol-related documents, such as the IRB-approved research protocol and informed consent document; and (b) the characteristics of the subject population being studied;
2. Related or possibly related to participation in the research (*possibly related* means there is a reasonable possibility that the incident, experience, or outcome may have been caused by the procedures involved in the research); and
3. Suggests that the research places subjects or others at a greater risk of harm (including physical, psychological, economic, or social harm) than was previously known or recognized.

A **Serious Adverse Event (SAE)** is defined as any untoward medical occurrence that results in death, is life-threatening, requires or prolongs hospitalization, causes persistent or significant disability/incapacity, results in congenital anomalies/birth defects, or, in the opinion of the investigators, represents other significant hazards or potentially serious harm to research participants or others.

Reporting Requirements

Study coordinators conduct medical record reviews at the regular study intervals coinciding with assessments (baseline, 6 week, and 6 month). Coordinators also review the medical record periodically (at 3 weeks, 18 weeks, 1 year) following the baseline assessment to determine if any anticipated AEs, SAEs, or UAEs occurred. Study staff are also informed to contact the site PI upon learning of a participant AE. The site PI reviews the AE to determine how to record and report the event, if applicable. Directing AE information to the site PI that is discovered separately from medical record review helps ensure that the study coordinator remains naïve to the treatment group (intervention or control). All AE reports are reviewed by the site PI before final documentation and submitting a report.

Notably, although the expected occurrence of non-study related anticipated AEs is high, the expected occurrence of study-related AEs associated with the intervention (participation in a group based self-management program), control (individual education support program), or study assessments (self-report questionnaires and cognitive testing) is low.

The VAPSHCS will evaluate the implications of AE information according to an identified protocol, specifically, the occurrence of 5 or more AEs or 2 or more SAEs will prompt a review of the study procedures for safety.

All anticipated AEs will be tracked and recorded on eCRFs used at regular study assessments, as well as at intervals of scheduled chart reviews. Study staff are trained to follow VA Central IRB reporting requirements for unanticipated SAEs and UAPs involving risks to participants or others. Reports must be submitted on the template (See Appendix F) to the VA Central IRB within 5 business days after the study staff becomes aware of the event. Additionally, site study staff (coordinators and PIs) should receive a copy of the SAE/UAP report.

All AEs (includes anticipated AEs, UAEs, UAPs, and SAEs) must be followed until resolution or a stable endpoint is reached, such as:

- AE is resolved and has returned to normal/baseline values or has stabilized.
- Subject is lost to follow-up or has withdrawn consent.
- AE is judged by the site PI, lead PI/SC, and/or Co-PI to be no longer clinically significant.
- Participant has completed study required follow-ups (6 month visit).

Additionally, the investigators will monitor all AEs and study activity. Although it is unlikely, the following conditions would trigger an immediate suspension of the research project:

- There was reason to believe the study procedures (assessments, intervention, control) were adversely affecting a participant's overall health, including mental health, as demonstrated by inpatient hospitalizations for mental health or suicide.
- The occurrence of 5 or more study-related AEs or 2 or more study-related SAEs in either condition will trigger a review of the protocols at the time of occurrence. It will better accommodate the expected low-base rate of problems and allow for the early identification issues than would a DSMB that met at an arbitrary regular interval.

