The study **project coordinator** is based at the Seattle site, and is primarily responsible for oversight of daily study operations at the five participating sites. The project coordinator also has regular contact with [name], the PI ([name]) and Co-PI ([name]) to assist in study troubleshooting with the site PIs and study coordinators as needed. The study project coordinator, with oversight from the PI and Co-PI, is responsible for submitting IRB materials to the VA Central IRB, including but not limited to: initial applications, protocol modifications, site correspondence, protocol deviations, and SAE reports. The project coordinator, along with [name], also monitors the site study coordinators and communicates with investigators to ensure efficient day-to-day study operations. The project coordinator will organize monthly teleconferences with site PIs and study coordinators to discuss progress, operations, and answer group operational questions as they arise.

Additionally, VAPSHCS project staff will conduct periodic site monitoring and quality assurance of each site to ensure that informed consent, training requirements, and adverse event monitoring are being routinely performed in strict accordance with the research protocol, requirements of the Central IRB, and local VA R&D committees. During the first 6 months of enrollment at each site, the project coordinator and/or Drs. [name] and [name] will conduct a virtual internal audit using the regulatory audit template from VAPSHCS. We will encourage each site to conduct an internal audit that adheres to their facility audit process to confirm both project wide and local facility compliance. We will also work to request a formal R&D audit during year 1, if possible, regardless of the local policy at each site.

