Enrolled participants are assigned on a rolling basis into successive cohorts of 8±2 individuals at each participating site. Each time 8±2 participants are enrolled, that cohort will be randomized 1:1 to receive either the VETPALS intervention or individual education support program (control condition). We will ensure that participants will not have completed a PALS program prior to study participation and will not be part of an existing PALS group during their study participation. Randomization will occur through an email exchange between the study sites (VETPALS facilitator or site PI) and the data manager at Spectrum Research. The data manager will maintain a randomization table that is stored locally on a server at Spectrum Research. When a cohort is ready for randomization, the facilitator or site PI will send an email to the data manager stating that a group of participants is ready for randomization. The email will also include a list of study ID numbers but will not contain any information that could identify participants. Within 12-24 hours of receiving the email, the data manager will verify the list of study IDs in the database to ensure all baseline assessments are complete, and then will obtain random assignment by accessing the randomization table. The data manager will respond via email to the facilitator or site PI with a value of 0 or 1 (0=individual education support program, 1=VETPALS). Both parties will retain a copy of the email for reference. The data manager will record the treatment assignment for the group in the randomization table, and the facilitator or site PI will record the treatment assignment in the randomization log. This method will ensure that treatment allocation is concealed during the recruitment of each cohort. A balanced number of groups will be randomly assigned to each site based on the projected enrollment at that site, which is a common randomization schedule used in group-based interventions. The randomization schedule and algorithm will not be shared with local sites to maintain concealment of treatment allocation. Additionally, the data manager will record a value of 0 or 1 to each study ID in the database which is linked to the study ID assigned at enrollment. Clinical research staff at each location (applicable investigators and VETPALS facilitators) will receive the treatment allocation and randomization ID in order to proceed with the treatment, intervention or control. Site study coordinators who conduct the baseline and follow-up assessments are blind to treatment.

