Participants will be randomized to a treatment group (group-based program/intervention vs. individual education program/control) following completion of the baseline assessment (see 5.1 Study Design). The site study coordinators will be naïve to treatment allocation throughout all of the assessments to minimize potential bias of the outcomes.

Group based self-management program (VETPALS Intervention)

Participants randomized to the intervention group will be asked to complete a checklist about their use of supplementary class resources, a checklist about their satisfaction with the classes, and selected participants will be invited to participate in a focus group to respond to and discuss implementation variables. The site PIs and VETPALS facilitator have primary responsibility in overseeing data collection on paper forms. Data will be entered into the central study database by the site PIs and/or VETPALS facilitator via eCRF. In the event a participant doesn't receive

any necessary materials during class sessions, a facilitator will mail materials to the participant and will include a return postage-paid addressed envelope if needed. Participants randomized to the intervention group are offered the other program at the end of their 6-month follow-up assessment. Study coordinators will record (yes/no) patients who elect to participate in the individual program and will refer patients to the facilitator who will discuss the other program and scheduling in more detail.

We will use a digital voice recorder to audio-record the VETPALS sessions. The purpose of audio-recording the VETPALS sessions is to monitor treatment fidelity, assess feedback, and ensure protocol adherence. Each participating site will consult with the local R&D office to ensure that the digital audio-recorder meets local VA guidelines, and all recorders will use FIPS 140-2 validated encryption. Sites will use the device(s) listed in the local site Central IRB applications.

Individual education support program (Control)

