In the event a site study coordinator is unavailable (e.g. planned absence) the site study coordinator and/or project coordinator from the lead site (VA Puget Sound Health Care System, Seattle, WA) may conduct baseline, medical record review, and follow-up assessments by telephone. Site study staff will inform participants of this temporary change by mailing or hand delivering a letter that explains the site study coordinator's absence. Participant study ID number, name, and phone number will be shared with the Seattle site study coordinator and/or project coordinator. Local site staff will contact Seattle staff by telephone or PKI-encrypted email to share this information. All information from other sites will be stored in accordance with this study protocol. See section 7.0 Privacy and Confidentiality for more details.

Participant Assessment Measures

All data are collected using EDC. Measures are displayed on a computer screen and site study coordinators and/or participants respond using VA approved and secure computers and responses are automatically placed in the study database. There are no paper CRFs for baseline and follow-up assessments as all questionnaires are displayed on eCRFs. In the event of a technical problem, data will be recorded on paper CRFs and transferred to an eCRF. The coordinator will use a secure shredding bin to discard the paper CRF the eCRF is complete. A description of each measure used is below, followed by Table 2, which displays a summary of the baseline and follow-up assessments.

Primary Outcomes

Physical functioning will be measured using the Musculoskeletal Function Assessment Short Form (MFA-SF). The MFA-SF is a 46-item questionnaire designed to measure functional status across a broad range of musculoskeletal disorders. Participants are asked to rate difficulties associated with daily activities ranging from "not at all difficult" to "unable to do," as well as the frequency of problems, ranging from "none of the time" to "all of the time." Responses are combined into a single physical functioning score. Twelve of the items constitute a separate subscale examining how much individuals are bothered by their limitations. This scale will also be computed, but is not the primary outcome. The MFA-SF has been utilized extensively in research,⁴³ and has established validity, reliability.⁴⁴

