- Discuss any AEs and SAEs during monthly teleconference meetings and review reporting requirements as necessary.

*Site IRB approval letters will be issued by VA Central IRB. VA Central IRB is the IRB of record for all participating study sites. Sites will submit the study to their local R&D Committee for review and approval.

Additional details on site communications for this VA multi-site study can be found in the *Protocol-Supplement for Multi-Site Studies Overseen by the VA Central IRB* (Appendix G).

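### Unmasked SAE/UAP report copies go to blinded outcome assessors, and the role that submits SAE reports may cover assessments, so safety reporting may reveal the arm

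*Combined protocol and SAP*

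**What the plan says.** **Blinding.** Section 5.1 (Study Design) states: "Site study coordinators who conduct the baseline and follow-up assessments are blind to treatment". Section 5.5 (Randomization) repeats it, "The site study coordinators will be naïve to treatment allocation throughout all of the assessments", and gives limiting outcome bias as the reason. Section 5.0 says the same of the site coordinators.

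**Safety information.** Section 6.1 (Reporting Requirements) contains a safeguard: "Directing AE information to the site PI that is discovered separately from medical record review helps ensure that the study coordinator remains" unaware of the arm. Later in the same subsection, after describing Central IRB reports of unanticipated SAEs and UAPs, it adds: "Additionally, site study staff (coordinators and PIs) should receive a copy of the SAE/UAP report".

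**Project coordinator.** Section 5.0 makes this role responsible for submitting IRB material, including "initial applications, protocol modifications, site correspondence, protocol deviations, and SAE reports". Section 5.5 (Temporary changes) says that when a site coordinator is unavailable, "the site study coordinator and/or project coordinator from the lead site (VA Puget Sound Health Care System, Seattle, WA) may conduct baseline", record-review and follow-up assessments by telephone. Section 8.0 repeats the arrangement.

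**Monthly calls.** Section 9.0 (Site Communications) includes: "Discuss any AEs and SAEs during monthly teleconference meetings and review reporting requirements as necessary". It does not say which meeting is meant.

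**The concern.** Participants know whether they attended classes, so the coordinator's blindness is the protection against assessment bias that this plan relies on. The copy rule gives the people who administer the primary outcomes a document that may describe what happened in the participant's arm, and so works against the safeguard stated earlier in the same subsection. Cluster allocation widens the effect: knowing one participant's arm means knowing the cohort's. The project coordinator raises the same problem from the other side, as someone who handles SAE reports and may then interview participants for outcomes.

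**Working it through.** The plan states no figure on this point, so the check sets the sections side by side.

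1. **Who has to be blind.** Sections 5.0, 5.1 and 5.5 all name site or study coordinators. They conduct the baseline, 6-week and 6-month assessments, which include the MFA-SF and PHQ-9 (section 5.5, Table 2). None of these statements names the project coordinator.

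2. **The two rules in section 6.1.** The first covers event information learned outside record review: it goes to the site PI so that the coordinator stays blind. The second sends coordinators a copy of the SAE/UAP report. It carries no condition about masking, redaction or waiting until the 6-month assessment. Site PIs review AE reports before submission, but nothing tells them to remove arm information.

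3. **What a report may show.** A UAP must be "Related or possibly related to participation in the research". Section 6.1 lists three possible sources of study-related events: the intervention, the control program, and the assessments. The first two differ plainly between arms (group sessions against individual materials and a call, section 5.1), so a narrative about either points to the arm. The third is common to both arms and does not. An unanticipated SAE need not be study-related at all. A report may therefore reveal the arm; it need not.

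4. **Reach of one revealing report.** Cohorts are 8±2, so 6 to 10 people. Against the enrollment target of 472: 6/472 = 1.3% and 10/472 = 2.1%. Coordinators can link cohort members, because they schedule baselines as a cohort fills (section 5.1) and alert the site PI when the group has finished baseline (section 8.0). A report seen before week 6 can affect both follow-ups; one seen between week 6 and month 6 affects only the later one; one seen afterwards affects no outcome.

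5. **Number of such reports.** The documents give none. Expedited reports are limited to unanticipated SAEs and UAPs, and section 6.1 classes re-hospitalization, further amputation, stroke, myocardial infarction, infection and death as anticipated. It also expects study-related events to be uncommon. The per-report reach in step 4 therefore cannot be multiplied up to a trial-level percentage.

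6. **Project coordinator.** Section 5.0 gives this role the submission of SAE reports for the study. Sections 5.5 and 8.0 allow it to conduct assessments as temporary cover. No section states that the role is blind, or bars it from assessing participants whose reports it handled.

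7. **Monthly calls.** Section 9.0 (General Communications) describes two: one for site PIs and coordinators, on progress, recruitment and retention; and one for site PIs, facilitators and other investigators, which explicitly covers AEs, SAEs and UAPs. Section 5.0 uses the word teleconference for the call that includes coordinators. The Site Communications item uses the same word without naming a meeting, so either reading is open.

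**The case against.** The case against is mainly about size. Few events would produce a report, and many of those reports would be silent on arm. The report template (Appendix F) is not in the documents, so it cannot be shown that reports name the arm. The primary outcomes are self-reported, and participants seen in person may enter answers themselves at a computer. They also know their own arm, so an occasional unblinded interviewer may add little bias. The project coordinator submits rather than necessarily writes the reports, covers only temporarily, and has no access to the randomization logs, which section 8.0 restricts to the site PI and facilitator.

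Most of this stands as a limit on magnitude. It does not remove the conflict. Telephone interviews are conducted and recorded by the coordinator, and the plan itself treats coordinator blindness as worth protecting.

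Two stronger readings are tempting. A reader might infer that every UAP report must disclose the arm, since a UAP must be related to the research; but the definition refers to participation in the research, which includes assessments shared by both arms. A reader might also take it as settled that coordinators hear SAE details on the monthly call; the documents leave this ambiguous, and the only agenda that names SAEs belongs to the investigator-level meeting.

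**Conclusion.** The point holds as an internal conflict worth correcting. Section 6.1 sends blinded assessors unmasked, undelayed report copies, against its own safeguard, and the project coordinator's two functions are combined without any stated blinding. The teleconference item is an ambiguity to close, not an established leak.

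Each arm-revealing report could expose the 6-10 members of one cohort, assuming that the narrative describes an arm-specific procedure, that the coordinator links the participant to the cohort, and that outcomes are still to be collected. A reader might go on to assume several such reports and state a share of the trial that would be unblinded. The documents give no expected number and point to a low one, so no such percentage is supported.

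A related matter needs its own reconciliation and is probably the larger route: section 6.1 has coordinators reviewing medical records during follow-up, while section 5.1 keeps them out of the record until follow-up is complete, and VETPALS sessions are entered there as appointments.

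**What to change.** - **Section 6.1 (Reporting Requirements):** send the full copy to the site PI only. Give coordinators an ID-only or arm-masked notice, or hold their copy until the cohort's 6-month assessments are complete. Section 5.5 already uses ID-only notification when a participant moves to a later cohort, so the device is not new to this plan.
- **Section 9.0 (Site Communications):** name the investigator-level monthly meeting as the place for AE and SAE discussion.
- **Sections 5.5 (Temporary changes) and 8.0:** restrict cover assessments to a blinded coordinator who does not handle SAE reports. Both sections must change, or a new contradiction appears. Section 5.0 should not be relied on for this: it permits the Seattle site coordinator to cover by telephone but does not exclude anyone else.

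The cost is protocol and operations-manual wording. No staff are added, and reporting to the Central IRB is unchanged. Coordinators would see less safety detail, and one back-up assessor would be lost.
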